### **3.4 Analysis Populations**

#### **3.4.1 Efficacy Analysis Population**

The FAS population will serve as the primary population for the efficacy data analysis. The FAS population consists of all randomized participants who received at least one injection of study intervention. Participants will be analyzed by the treatment group assigned at randomization.

#### **3.4.2 Safety Analysis Population**

The APaT population will be used for the safety data analysis. The APaT population consists of all randomized/allocated participants who received at least one injection of study intervention. Participants will be analyzed in the treatment arm actually received.

#### **3.4.3 Pharmacokinetic Analysis Population**

The population for PK data analysis will include all participants with at least 1 measurable PK sample after treatment with MK-6194.

#### **3.4.4 Pharmacodynamic Analysis Population**

The population for the PD endpoints will be the FAS population. All randomized participants who have at least 1 injection (including partial injection) of study intervention and have at least 1 assessment for those analyses for which this is required will be included in this population.

#### **3.4.5 Immunogenicity Analysis Population**

The population for immunogenicity analysis will include all participants with at least 1 ADA assay result after treatment with MK-6194.

### **3.5 Statistical Methods**

Efficacy results that will be deemed to be statistically significant after consideration of the Type-I error control strategy are described in Section 3.7 of the SAP.

#### **3.5.1 Estimand(s)**

*Estimand for the Primary Efficacy Analysis*

The estimand for the primary objective of this study contains 5 attributes:

- Treatment Regimen: MK-6194 or matching placebo
- Target population: Adult with Non-Segmental Vitiligo
- Endpoint: The percent change from baseline in F-VASI at Week 24
- Population-level summary: the difference in the mean percent change from baseline in F-VASI at Week 24 between the treatment group and placebo

- Intercurrent events: Detailed below:

Number	Intercurrent Events	Handling Strategy
Intercurrent Event #1	Discontinuation of MK-6194 or placebo	Treatment Policy Strategy
Intercurrent Event #2	Usage of any medication for the treatment of Vitiligo as listed in Protocol Section 5.2 # 19	Treatment Policy Strategy

### 3.5.2 Statistical Methods for Efficacy Analyses

All efficacy endpoints will be analyzed based on the FAS population. Unless otherwise specified, all efficacy data will be included in efficacy analyses. A Hochberg testing procedure will be implemented in this study for multiplicity adjustment. LDA method will be used for the analysis of the continuous endpoints, and stratified M&N method will be used for the analysis of the binary endpoints.

#### **Primary Efficacy Analysis**

The primary endpoint, the percent change from baseline in F-VASI score at Week 24, will be analyzed using a LDA model for repeated measures. This model will use all available data on F-VASI at baseline and all post-baseline timepoints up to Week 24. In this model, time will be treated as a categorical variable so that no restriction is imposed on the trajectory of the means over time. The analysis model will adjust for treatment, visit, treatment by visit, and baseline vitiligo status (stable, active) and previous JAK inhibitor use (yes, no) based on IRT values. The treatment difference in terms of the mean percent change from baseline at Week 24 will be estimated and tested from this model. Point estimates, 95% CI and p-value for the treatment differences will be provided. An unstructured covariance matrix will be used to model the correlation among repeated measurements. If the unstructured covariance structure fails to converge with the default algorithm, an autoregressive AR(1) or compound symmetric (CS) structure will be used. The LDA method assumes that the mechanism for missing data is MAR. In this study, it is expected that MAR/MCAR mechanisms will underlie most of the missingness, and the proportion of data that are MNAR, driven solely by unobserved values of the study endpoints, will be small. Reasons for discontinuation from the study may include lack of efficacy, AEs, relocation, withdrawal of consent and protocol deviations. Missing data caused by a participant's relocation or data processing issues are likely to be MCAR. Missing data caused by discontinuations due to lack of efficacy may belong to MAR because this type of discontinuation may depend on the observed efficacy outcomes. The MAR or MNAR mechanisms might each underlie the other reasons to some extent. If the assigned study intervention in large part determines the loss of data for these other reasons (such as AEs), the mechanism may be close to MAR since the intervention assignment is an observed variable and included in the analysis model.

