9.5.2 Statistical Methods for Efficacy Analyses

All efficacy endpoints will be analyzed based on the FAS population. Unless otherwise specified, all efficacy data will be included in efficacy analyses. A Hochberg testing procedure will be implemented in this study for multiplicity adjustment. LDA method will be used for the analysis of the continuous endpoints, and stratified M&N method will be used for the analysis of the binary endpoints.

Primary Efficacy Analysis

The primary endpoints, the percent change from baseline in F-VASI score at Week 24, will be analyzed using a LDA model for repeated measures. This model will use all available data on F-VASI at baseline and all post-baseline timepoints. In this model, time will be treated as a categorical variable so that no restriction is imposed on the trajectory of the means over time. The analysis model will adjust for treatment, visit, treatment by visit, and baseline vitiligo status (stable, active) and previous JAK inhibitor use (yes, no). Point estimates, 95% CI and p-value for the treatment differences will be provided. If there are a small number of responses in one or more strata, for the purpose of analysis, strata will be combined to ensure a sufficient number of participants and responses in each stratum. Details regarding the

combining of strata will be specified in the SAP prior to database lock based on a blinded review of response by stratum. An unstructured covariance matrix will be used to model the correlation among repeated measurements.

Sensitivity Analyses

In addition to the analysis approach specified above for the primary endpoint analysis section, the following sensitivity analyses will be used to assess the robustness of the primary analysis approach.

Multiple-imputation Analysis

For all participants with missing baseline F-VASI assessment, single imputation (only once) will be implemented based on baseline stratification factors. All post-baseline missing F-VASI assessments will be handled using multiple imputation (MI) under the missing-at-random (MAR) assumption.

Tipping-point Multiple-imputation Analysis

Tipping point as described in Ratitch et al. (2013) [Ratitch, B., et al 2013] will be conducted. In this approach, missing data are first imputed for all visits under the MAR assumption, and then the worsening/shift is applied. This is repeated with increasing the delta-shift (worsening) until the result is no longer statistically significant.

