### **Multiple-imputation Analysis**

For all participants who are missing baseline F-VASI assessment, single imputation (only once) will be implemented based on baseline vitiligo status (stable, active) and previous JAK inhibitor use (yes, no). All post-baseline missing F-VASI assessments will be handled using MI under the missing-at-random assumption.

A fully conditional specification method that assumes the existence of a joint distribution for all variables will be used. A regression model including treatment group, stratification factor(s) and percent change from baseline in F-VASI scores at all post-baseline visits up to Week 24 will be specified for the fully conditional specification method. The randomization seed will be set to 6194007. The MI procedure will be repeated 50 times and the imputed endpoint will be analyzed using the same analysis model as the primary analysis based on each of the datasets. SAS PROC MIANALYZE will be used to generate the final treatment differences between MK-6194 treatment group and placebo group and the statistical inferences, including hypothesis testing, and 95% CI will be combined using Rubin's rule.

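### Baseline F-VASI is not a covariate in the primary or imputation model, and its role in the percent-change analysis is left loosely worded

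*SAP*

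**What the plan says.** SAP 3.3.3 defines percent change as the visit value minus baseline, divided by baseline. SAP 3.5.2 states that "the percent change from baseline in F-VASI score at Week 24, will be analyzed using a LDA model for repeated measures", and continues: "This model will use all available data on F-VASI at baseline and all post-baseline timepoints up to Week 24". Protocol 9.5.2 has nearly the same sentence: "This model will use all available data on F-VASI at baseline and all post-baseline timepoints". The target of the model is explicit: "The treatment difference in terms of the mean percent change from baseline at Week 24 will be estimated and tested from this model". The terms are given as "The analysis model will adjust for treatment, visit, treatment by visit, and baseline vitiligo status (stable, active) and previous JAK inhibitor use (yes, no", with the strata taken from IRT. On covariance, "An unstructured covariance matrix will be used to model the correlation among repeated measurements"; if that does not converge, "an autoregressive AR(1) or compound symmetric (CS) structure will be used".

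The multiple-imputation sensitivity analysis uses "A regression model including treatment group, stratification factor(s) and percent change from baseline in F-VASI scores at all post-baseline visits", stopping at Week 24. The imputed endpoint is then analysed with the primary model. T-VASI is to be handled in a similar way.

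Baseline F-VASI appears in SAP 3.9 as a subgroup factor (below 1, or 1 and above). It is not a stratification factor in Protocol 6.3.2.

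**The concern.** There are two connected issues.

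First, the outcome's own baseline value is left out of the covariates. It costs nothing to collect: F-VASI is scored at screening and randomization (Protocol 1.3.1) and a minimum of 0.3 is an entry criterion (Protocol 5.1). Eligible scores can run from 0.3 to the scale maximum of 3.5 (Protocol 8.2.2), and the SAP already regards baseline level as worth a subgroup analysis. If baseline predicts percent change, omitting it leaves chance imbalance uncorrected and some precision unused.

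Second, the text does not say whether the response is the raw score or percent change. Nor does it say whether baseline enters as a row of the response, only as the denominator, or in some other way. For the one endpoint under formal testing, that should not be left to programming.

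**Working it through.** **Step 1. What role can baseline have?** F-VASI is scheduled at baseline and at Weeks 2, 4, 8, 12, 18 and 24 (Protocol 1.3.1), so there are six post-baseline visits. Three readings are possible.

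- *Percent change with a baseline row.* The baseline value is (b - b)/b x 100 = 0 for everyone. The 7 x 7 covariance matrix then has a zero row and column, rank 6 and determinant 0. An unstructured fit is singular.
- *Raw F-VASI including baseline.* This can be fitted, but the contrast is in score units and no conversion to mean percent change is given. The two scales can differ. In an illustration with assumed inputs (skewed baseline scores between 0.3 and 3.5, correlation 0.3 between baseline and percent change), mean percent change is -25.1% while the change in the mean score is -18.9%.
- *Percent change at post-baseline visits only.* This can be fitted and targets the stated quantity. Baseline serves only as the denominator, and the comparison is not adjusted for it.

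The imputation section names percent change at post-baseline visits and then applies the primary model. That favours the third reading.

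**Step 2. The plan's own power.** The inputs, from Protocol 9.8 and SAP 3.8, are 55 per arm, 15% dropout, a difference of -20, an SD of 33 and more than 80% power for at least one dose. The two-sided alpha is 0.0499 in the protocol; the SAP figure is partly masked.

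- Evaluable per arm: 55 x 0.85 = 46.75.
- Standard error: 33 x sqrt(2/46.75) = 6.83.
- Standardized effect: 20/6.83 = 2.93. Power for one comparison at 0.0499 is 83.4%.
- At least one dose under Hochberg, both doses at -20: about 89.1% (simulated test statistics, correlation 0.5 from the shared placebo arm, 1,000,000 runs).

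The plan's figure is reproduced with no baseline covariate.

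**Step 3. The gain from adjusting.** If baseline has correlation rho with Week 24 percent change, the adjusted SD is 33 x sqrt(1 - rho^2). The documents do not give rho, so a range is assumed.

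| rho | variance removed | adjusted SD | one comparison at 0.0499 | at least one dose, both at -20 |
|---|---|---|---|---|
| 0 | 0% | 33.0 | 83.4% | 89.1% |
| 0.1 | 1% | 32.83 | 83.8% | 89.5% |
| 0.2 | 4% | 32.33 | 84.8% | 90.4% |
| 0.3 | 9% | 31.48 | 86.7% | 91.8% |

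The largest gain in the last column is 91.8 - 89.1 = 2.7 points. If only one dose has the -20 effect, power for at least one dose goes from about 75.8% at rho 0 to 79.9% at rho 0.3, roughly 4 points.

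**The case against.** The strongest reply is that nothing here is invalid. The SAP speaks of F-VASI data at baseline, not of percent change at baseline, and baseline scores are needed anyway to form every percent change. The imputation section describes a fittable post-baseline response. Treatment is randomized, both stratification factors are in the model, and chance imbalance in baseline score does not bias the comparison or invalidate its test. The size of any gain rests on a correlation that nobody has documented. All of this stands.

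A reader might go further and infer that the model is degenerate as written and must drop to the AR(1) or compound symmetric fallback. The documents do not support that. Singularity arises only if a constant 0 is entered as a baseline response row, which the text does not say and the imputation section argues against. A reader might also infer that the analysis is on the wrong scale. The stated contrast and the estimand in SAP 3.5.1 both name mean percent change, which argues against a raw-score response.

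The reply does not dispose of the omission itself. Dividing by baseline is not covariate adjustment, and neither is a subgroup table. Even on a raw-score reading, a free treatment effect with no stated constraint of equal baseline means would bring no gain of the analysis-of-covariance kind. Part of SAP 3.3.3 is masked and SAP section 2 refers to a separate analysis specification, so baseline's role may be settled in material that cannot be seen.

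**Conclusion.** The point holds as an inexpensive improvement with a clarification attached, not as an error that invalidates the primary analysis. Baseline F-VASI is absent from the covariates of both the primary and the imputation model, and the sentence about baseline data does not sit well with a percent-change response. On the best-supported reading the comparison is valid but unadjusted for baseline.

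The benefit is rho-squared of the variance. For an assumed rho of 0 to 0.3 and both doses at -20, that is nil to about 3 points of power for at least one dose. The calculation assumes a common SD of 33, 46.75 evaluable per arm and a linear relation with baseline. It would be wrong to call the gain assured, since rho may be near zero, or to say that the stated power of more than 80% depends on it.

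**What to change.** In Protocol 9.5.2 and SAP 3.5.2:

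- Define the response as percent change at post-baseline visits only, which for F-VASI are Weeks 2, 4, 8, 12, 18 and 24. Replace the sentence on baseline data so that baseline is no longer part of the response vector.
- Add continuous baseline F-VASI and its interaction with visit to the primary model.
- Add baseline F-VASI to the imputation model, so that it carries every variable used in the analysis model.
- Do the same for T-VASI with baseline T-VASI, at its own scheduled visits: Weeks 4, 12, 18 and 24. Protocol 1.3.1 has no T-VASI at Weeks 2 or 8.

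The opening text of Protocol section 9 and SAP section 3 sends changes in the primary method made before unblinding through a protocol amendment, so a SAP edit alone is not enough. The cost is that amendment, matching SAP text and six extra fixed-effect parameters for F-VASI (one baseline slope per visit). No new data are needed.

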6.3.2 Stratification

Intervention randomization will be stratified according to the following factors:

1. Stable vs active vitiligo

Treatment response in active versus stable vitiligo might be different.

- Active vitiligo is defined as new/extending lesion(s) in the 6 months prior to Screening Visit (confirmed by photographs or medical record/history) and/or; confetti-like lesion(s); trichrome lesion(s); Koebner phenomenon/phenomena (excluding Type 1 [history based on isomorphic reaction]), inflammatory vitiligo.
- Stable vitiligo is defined as an absence of signs of active disease (no signs of new or extending lesions).

2. *Previous JAKi exposure (yes or no)*

- It is unknown whether exposure to JAKi may affect response to an IL-2 mutein or if an inadequate response to JAKi may predict an inadequate response to MK-6194.

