9.8 Sample Size and Power Calculations

This study will randomize 55 participants into each treatment group and has >80% power to demonstrate the superiority of at least 1 dose of MK-6194 over placebo at an overall 2-sided 0.0499 alpha-level, if the underlying treatment difference in percent change from baseline at Week 24 in F-VASI score is -20%. The power and sample size are based on the following assumptions: 1) a 15% drop out rate, 2) a standard deviation of 33%, pooled across treatment groups.

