## **Secondary Efficacy Analysis**

The secondary efficacy endpoint, the percent change from baseline in T-VASI at Week 24, will be analyzed similarly as the primary endpoint.

[Table 2](#) summarizes the analysis strategy of the primary and secondary efficacy endpoints.

Table 2 Analysis Strategy for Key Efficacy Variables

Endpoint/Variable (Description, Time Point)	Primary vs Supportive Approach	Statistical Method	Analysis Population	Missing Data Approach
Primary Endpoint/Hypothesis 1				
Percent change from baseline in F-VASI at Week 24	P	LDA	FAS	Model based
	S	LDA	FAS	Multiple Imputation
	S	LDA	FAS	Tipping Point Multiple Imputation
Secondary Endpoint 2				
Percent change from baseline in T-VASI at Week 24	P	LDA	FAS	Model based
FAS=Full Analysis Set; F-VASI= Facial Vitiligo Area Scoring Index; LDA=longitudinal data analysis; T-VASI= Total Vitiligo Area Scoring Index P=Primary approach; S=Supportive approach.				

The efficacy analysis mentioned above will be performed at the end of the Double-Blind Treatment Period (Week 24). Additional descriptive analyses will be performed at the end of the Blinded Extension Period (Week 52). No comparison between treatment groups will be involved in any of the analyses for blinded extension. Details of the analysis plan will be finalized in the SAP before the final database lock.

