### **3.7 Multiplicity**

If the interim analysis for futility is conducted, an  $\alpha$ -spending of 0.0001 will be applied to the 2-sided Type I error rate of 5% for the primary hypothesis based on the Haybittle-Peto method [Haybittle, J. L. 1971] [Peto, R., et al 1976]. Multiplicity adjustment will be made for testing 2 doses on the primary endpoint for the analysis, i.e., for testing a family of the following hypotheses:

- H1(1): 3 mg MK-6194 Q4W dose is superior to placebo in the percent change from baseline in F-VASI at Week 24.
- H1(2): 3 mg MK-6194 Q2W dose is superior to placebo in the percent change from baseline in F-VASI at Week 24.

To strongly control the Type-I error rate for this family, the Hochberg procedure [Hochberg, Y. 1988] will be applied.

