### 3.8 Sample Size and Power Calculations

This study will randomize 55 participants in each treatment group and has >80% power to demonstrate the superiority of at least 1 dose of MK-6194 over placebo at an overall 2-sided 0.05 PPD alpha-level, if the underlying treatment difference in percent change from baseline at Week 24 in F-VASI score is -20%. The power and sample size are based on the following assumptions: 1) a 15% drop out rate, 2) a standard deviation of 33%, pooled across treatment groups.

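### The primary model gives each stratification factor one effect for all visits, so if stratum effects build over time the Week 24 comparison is under-adjusted and its standard error somewhat too large

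*SAP*

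**What the plan says.** SAP 3.5.2 (Primary Efficacy Analysis) lists the fixed terms: "The analysis model will adjust for treatment, visit, treatment by visit, and baseline vitiligo status (stable, active) and previous JAK inhibitor use (yes, no"). Protocol 9.5.2 has the same list. Neither document has a stratum-by-visit term. Because the treatment-by-visit product is written out, the two strata are naturally read as main effects only.

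On the data and covariance, the SAP says "This model will use all available data on F-VASI at baseline and all post-baseline timepoints up to Week 24" and "An unstructured covariance matrix will be used to model the correlation among repeated measurements", with AR(1) or compound symmetry as fallback. The Schedule of Activities (protocol 1.3.1) puts post-baseline F-VASI at Weeks 2, 4, 8, 12, 18 and 24.

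T-VASI "will be analyzed similarly as the primary endpoint", so it inherits the same terms. In the multiple-imputation analyses each completed dataset is also analysed with the primary model.

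On why vitiligo status is a stratification factor, protocol 6.3.2 says: "Treatment response in active versus stable vitiligo might be different". For previous JAKi exposure it says only that the influence is unknown.

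**The concern.** The response is percent change from baseline, which is zero for everyone at the start. If active and stable disease, or JAKi-exposed and unexposed participants, follow different courses, the gap should be small at Week 2 and largest at Week 24. One coefficient per factor forces the gap to be equal at every visit. This sits oddly with the SAP's decision to treat time as categorical so that mean profiles are unconstrained.

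Generalised least squares weights the visits by precision. If early visits have small variance, they determine the common coefficient and it lands near zero. The between-stratum variation at Week 24 then stays in the residual. Stratified randomisation has already removed that variation from the true sampling error of the treatment difference, so the reported SE exceeds the real one. At stake is some efficiency at the one visit that is tested, on factors the trial went to the trouble of stratifying by.

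**Working it through.** **Inputs from the documents** (SAP 3.8, protocol 9.8): 55 per arm, 15% drop-out (55 × 0.85 = 46.75), difference 20, SD 33. Protocol 9.8 works "at an overall 2-sided 0.0499 alpha-level". SAP 3.7 makes the 0.0001 deduction conditional ("If the interim analysis for futility is conducted"). The results below are practically the same at 0.05.

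**Assumptions, not in the documents:** two independent 50/50 factors. Each has a Week 24 difference d of 5, 10, 15 or 20 points, growing linearly from zero. Total Week 24 SD is held at 33. Within-stratum SD grows with time (square root or linear), with adjacent-visit correlation 0.7 or 0.85, decaying with distance.

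**1. The plan's own figure.** SE = 33 × √(2/46.75) = 6.83; 20/6.83 = 2.93; power = Φ(2.93 − 1.96) = 83.4% for one comparison. With both doses at −20, Hochberg power for at least one dose is 89.2%. Both agree with the SAP's claim that the study "has >80% power to demonstrate the superiority of at least 1 dose of MK-6194 over placebo".

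**2. True sampling SE under stratified randomisation.** A 50/50 factor with difference d contributes d²/4 to the variance, so two contribute d²/2. Within-stratum SD = √(1089 − d²/2), and the true SE is that times √(2/46.75).

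**3. The common coefficient.** In large samples c = (1′Ω⁻¹δ)/(1′Ω⁻¹1). Here δ holds the true effects by visit and Ω is the fitted residual covariance, including the misfit. Under the assumptions above c is about 0.3 to 1.2 when the Week 24 effect is 10, and about 0.7 to 2.5 when it is 20.

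**4. Model SE at Week 24.** Residual variance = within-stratum variance + (d − c)²/2.
- d = 10, c = 0.3: 1039 + 47.0 = 1086.0, SD 32.95, against 32.23: ratio 1.022. With c = 1.2: 1039 + 38.7 = 1077.7, SD 32.83: ratio 1.019.
- d = 20, c = 0.7: 889 + 186.2 = 1075.2, SD 32.79, against 29.82: ratio 1.10. With c = 2.5: 889 + 153.1 = 1042.1, SD 32.28: ratio 1.08.

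**5. Power and level.** With k the SE ratio, the plan's model has power Φ(20/SE − 1.961k) and a model with visit-specific strata has Φ(20/SE − 1.961), where SE is the true one. The actual two-sided level is 2(1 − Φ(1.961k)).

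| d per factor | Share of Week 24 variance | True SE | k | Power, plan | Power, visit-specific | Actual level, plan |
|---|---|---|---|---|---|---|
| 5 | 1.1% | 6.79 | 1.005 | 83.6% | 83.8% | 4.9% |
| 10 | 4.6% | 6.67 | 1.02 | 84.1% | 85.1% | 4.5% |
| 15 | 10.3% | 6.46 | 1.05 | 85.0% | 87.2% | 4.0% |
| 20 | 18.4% | 6.17 | 1.08-1.10 | 86.1-87.0% | 90.0% | 3.1-3.4% |

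**6. Simulation.** 600 trials per scenario, 55 per arm, stratified blocks, 15% monotone drop-out, unstructured covariance, for d = 0 / 10 / 20:
- Plan's model: mean SE 6.67 / 6.65 / 6.64 against empirical SD 6.69 / 6.42 / 6.02; single-comparison power 86.8 / 85.7 / 86.7%.
- Visit-specific strata: mean SE 6.63 / 6.47 / 5.98 against empirical SD 6.68 / 6.41 / 6.00; power 86.8 / 87.2 / 90.3%.

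The empirical SDs of the two models agree, so the plan's estimator is about as precise and only its reported SE is too large. All mean estimates were within 0.25 of −20.

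**7. Sensitivity to the unstated patterns.** With SDs flat across visits the common coefficient recovers about half the effect (4.7 to 5.4 of 10), and the SE excess is 0.5-0.7% at d = 10 and about 2-3% at d = 20. If the stratum effect is absent, or equal at every visit, the excess is zero. In the other direction, equal correlation between all visits with growing SD gives 2.7% at d = 10 and 12% at d = 20, or 3.4% and 15% if the effect builds late. In the last case the plan's power is still Φ(3.243 − 1.961 × 1.152) = 83.7%.

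**The case against.** The strongest reply is that the whole loss is hypothetical. Neither document gives a stratum effect or an SD at any visit. Protocol 6.3.2 speaks of a possible difference in response to treatment, which is effect modification and is covered by the subgroup analyses in SAP 3.9. It does not establish that the strata predict outcome in every arm. For JAKi exposure the protocol claims no direction at all. This stands, and it is why the result is given as a range.

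The upper end is also demanding. A 20-point difference for each factor equals the assumed drug effect. A 50/50 JAKi split is the most that the enrolment cap of about 50% allows. Early SDs may not be small either. Entry permits an F-VASI of 0.3, and one fully depigmented fingertip unit scores 0.03, or 10% of that baseline, so scoring noise could raise early variance and weaken the pull. These points favour the lower part of the range.

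A reader might infer more than the documents support:
- That the trial is underpowered. It is not shown. The SD of 33 is pooled across treatment groups and is not described as within-stratum, so the power statement takes no credit for stratum adjustment. The plan's single-comparison power stays above 80% in every scenario. If only one regimen works, Hochberg tests it at about half alpha and power is about 75.5% with non-prognostic strata; that is a separate matter.
- That type I error is inflated. The error runs the other way.
- That the Week 24 estimate is biased. The simulation showed none. A shift of about 0.4 to 1 point needs 15% placebo drop-out concentrated in one stratum, and is small beside an SE near 6.8.

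**Conclusion.** The point holds as a conditional efficiency concern. As written, the model cannot represent a stratum effect that grows over the visits. If such an effect exists and variance grows too, Week 24 is analysed almost as though unadjusted, with an SE overstated by about 0.5%, 2%, 5% and 8-10% for differences of 5, 10, 15 and 20 points per factor. The cost is under 1, about 1, about 2 and about 3-4 points of single-comparison power, measured against a better model and not against the plan's own claim. These figures rest on 50/50 independent factors, a Week 24 SD of 33 and correlation that decays between visits. Flat SDs make the loss much smaller, equal correlations make it larger, and non-prognostic or visit-constant strata make it zero. T-VASI carries the same weakness by reference, though its size was not computed.

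**What to change.** In protocol 9.5.2 and SAP 3.5.2, add vitiligo status-by-visit and previous JAKi use-by-visit to the listed terms. Use the same mean model for T-VASI and for the analysis of each imputed dataset, including the tipping-point analysis. The imputation regression already includes the stratification factors and can stay. The estimand, unstructured covariance and Week 24 contrast do not change.

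The cost is 2 factors × 5 further visits = 10 mean parameters for F-VASI, and 2 × 3 = 6 for T-VASI (Weeks 4, 12, 18 and 24), with a slightly greater convergence burden. With about 165 participants this is minor; with non-prognostic strata the simulation showed no loss of single-comparison power. No new data are needed. The change concerns the method for the primary hypothesis, so the introductions to protocol Section 9 and SAP Section 3 require a protocol amendment before any unblinding, with the SAP updated to match.
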